9.2 Safety Assessments

Safety assessments will be based on AEs, concomitant medications, and limited clinical laboratory parameters (hematology and chemistry).

9.3 Study Procedures

9.3.1 Schedule of Events

Table 1 presents the complete schedule of events with details following in text.

Additional procedures may be performed as part of standard of care but the performance and outcome of these assessments will not be collected as part of this study.

Note any deviation from protocol procedures. Investigators are responsible for implementing appropriate measures to prevent the recurrence of violations and deviations and to report to their Institutional Review Board / Independent Ethics Committee (IRB/IEC) according to policy.

Table 1: Schedule of Events

| | Screening | Each 28-day Cycle Day | | | | | Treatment Discontinuation/ |
|---|------------------------|--------------------------|---|---|---|---|----------------------------------|
| | (Day -14 to Day -1) | 1 | 2 | 3 | 4 | 5 | Safety Follow Up ^a |
| Procedures | | | | | | | |
| Informed consent | X | | | | | | |
| Physical examination ^b | X | | | | | | |
| Hematology ^c | X | X | | | | | X |
| Serum chemistry ^d | X | X | | | | | X |
| Serum or urine pregnancy test ^e | X | X | | | | | X |
| Investigator's confirmation of eligibility | x | | | | | | |
| Weight | X | X | | | | | |
| Height | X | | | | | | |
| BSA calculation ^f | X | Xf | | | | | |
| Guadecitabine treatment | | X | X | X | X | X | |
| Adverse events | | X | X | X | X | X | X |
| Concomitant medications | | X | X | X | X | X | X |
| Survival status | | | | | | | X |

To be performed 30±7 days after the last guadecitabine dose or prior to the subject receiving alternative anticancer therapy, whichever comes first. If the subject cannot attend the clinic, the visit may be conducted by telephone to collect, at minimum, AE information.

- b Complete physical examination includes weight and examination of body systems according to institutional standards. A complete physical examination is required.
- ^e Hematology parameters will be limited to those identified in Table 2. Day 1 hematology for Cycle 1 does not need to be repeated if screening is done within 1 week of Cycle 1 Day 1. Collection, analysis, and reporting information are described in the Study Lab Manual.
- Serum chemistry parameters will be limited to creatinine and liver function tests, as identified in Table 2. Day 1 serum chemistry for Cycle 1 does not need to be repeated if screening is done within 2 weeks of Cycle 1 Day 1. Collection, analysis, and reporting information are described in the Study Lab Manual.
- Women of child-bearing potential only. The screening test must be done within 7 days of Cycle 1 Day 1; test not required on Cycle 1 Day 1 if done at screening.
- f Weigh subjects on Day 1 of each cycle. BSA recalculation is only required if weight changes ±10% or more from the last calculation.

9.3.2 Screening Procedures

After the investigator or sub-investigator confirms that a subject is eligible and willing to participate in the study, study center personnel will forward the appropriate documentation to the attention of the sponsor according to the study manual.

Within 14 days before treatment administration, perform the following study procedures and tests:

 Written informed consent. The informed consent form (ICF) must be signed and dated by the subjects before any study-specific samples are collected or study-specific procedures are initiated.

- Complete physical exam including height and weight, and examination of body systems according to institutional standards.
- Serum or urine pregnancy test: for women of child-bearing potential only. Must be done within 7 days of Cycle 1 Day 1. Results must be negative for the subject to be eligible for enrollment into the study.
- Sample collection for clinical laboratory tests (hematology and serum chemistry; Table 2).
 Collection, analysis, and reporting information are described in the Study Lab Manual.
- BSA calculation.
- Investigator's confirmation of eligibility and favorable benefit/risk assessment for the subject.
 Perform all necessary procedures and evaluations to document that the subject meets each eligibility criterion.

Table 2: Clinical Laboratory Tests

| Hematology | Serum Chemistry | Urinalysis | Serology |
|---|--|------------------|----------------------|
| - Complete blood count (CBC) | - Albumin | - Pregnancy test | - Pregnancy test (if |
| - Hemoglobin | Alkaline phosphatase | (if applicable) | applicable) |
| - RBC counts | - ALT | (| |
| - WBC counts | - AST | | |
| - Platelets | - Creatinine | | |
| Absolute neutrophil count | - Total bilirubin | | |
| | - Direct bilirubin (only if total | | |
| WBC differential | bilirubin is elevated) | | |

9.3.3 Treatment Procedures

Visits will occur on every treatment day (Days 1-5 of each 28-day cycle). The following procedures will be performed:

- Sample collection for clinical laboratory tests (Day 1 only) (Table 2), including hematology, serum chemistry, and pregnancy test for women of child-bearing potential (collect samples prior to guadecitabine treatment). For Cycle 1, Day 1 hematology and serum chemistry does not need to be repeated if screening is done within 1 week of Cycle 1 Day 1. Pregnancy test does not need to be repeated on Cycle 1 Day 1 if done at screening. Collection, analysis, and reporting information are described in the Study Lab Manual.
- Weight (Day 1 only). If weight has changed ±10% from the last measurement, BSA should be recalculated.
- Guadecitabine administration (Days 1-5).
- Adverse events and concomitant medications.

9.3.4 Treatment Discontinuation and Safety Follow-up Visit

Each subject should be followed up, to document the occurrence of any new AEs, for at least 30 (+7) days after his or her last dose of study treatment, or until any AE or SAE assessed as related to study treatment or procedures has resolved to a clinically acceptable or stable resolution (see Section 10.4). Subjects who withdraw consent should still be encouraged to complete this visit. If the subject is unable to attend the clinic, the visit may be conducted by telephone to collect AEs and survival status. If the subject discontinued guadecitabine treatment to receive alternative therapy, this visit should be conducted prior to the start of alternative therapy. The following evaluations are to be performed:

- Sample collection for clinical laboratory tests (Table 2), including hematology, serum chemistry, and pregnancy test for women of child-bearing potential. Collection, analysis, and reporting information are described in the Study Lab Manual.
- Adverse events and concomitant medications.
- Survival status.

10.0 EVALUATION, RECORDING, AND REPORTING OF ADVERSE EVENTS

10.1 Definitions

10.1.1 Adverse Event (AE)

Adverse Event (AE): Any untoward medical occurrence associated with the use of a drug in humans, whether or not considered drug related. An AE can therefore be any unfavorable and unintended sign (including a clinically significant abnormal finding in laboratory tests or other diagnostic procedures), symptom, or disease temporally associated with the use of a drug, without any judgment about causality. An AE can arise from any use of the drug and from any route of administration, formulation, or dose, including an overdose.

Disease progression is not considered to be an AE or serious adverse event (SAE). If there are specific AEs that are always part of disease progression, these do not need to be reported as AEs or SAEs. Pre-existing medical conditions (other than natural progression of the disease being studied) judged by the investigator or subject to have worsened in severity or frequency or changed in character during the protocol-specified AE reporting period will be reported as AEs or SAEs as appropriate.

An AE or SAE can also be a complication that occurs as a result of protocol mandated procedures (eg, invasive procedures such as biopsies).

10.1.2 Serious Adverse Events (SAEs)

An AE is considered serious, if in the view of either the investigator or sponsor, it results in any of the following outcomes:

- Death.
- A life-threatening AE.

An AE is considered "life-threatening" if in the view of either the investigator, or sponsor, its occurrence places the subject at immediate risk of death. It does not include an AE that, had it occurred in a more severe form, might have caused death.

- Inpatient hospitalization or prolongation of an existing hospitalization.
- A persistent or significant incapacity or substantial disruption of the ability to conduct normal life functions.
- A congenital anomaly or birth defect.

Important medical events that may not result in death, be life-threatening or require hospitalization may be considered serious when, based on the appropriate medical judgment, they may jeopardize the subject and may require medical or surgical intervention to prevent one of the outcomes listed in the definition of SAE. Examples of such medical events are intensive treatment in an emergency room or at home; blood dyscrasias or convulsions that do not result in inpatient hospitalization; or development of drug dependency or drug abuse.

10.2 Adverse Event Reporting and Descriptions

Record new AEs from the start of study treatment until 30 days after the last dose of study treatment or until the subject starts new anticancer treatment, including new investigational treatment, whichever occurs earlier.

Record all AEs either observed by the investigator or one of his or her medical collaborators, or reported by the subject spontaneously, or in response to the direct question below, in the AEs section of the subject's CRF/eCRF, in the source document, and if applicable, record on the SAE form. Whenever possible, the investigator should group signs and symptoms (including laboratory tests or other results of diagnostic procedures) into a single diagnosis under a single term. For example, cough, rhinitis, and sneezing might be reported as "upper respiratory infection" or a pulmonary infiltrate, positive sputum culture and fever might be reported as "pneumonia."

To optimize consistency of AE reporting across centers, ask the subject a standard, general, non-leading question to elicit any AEs (such as "Have you had any new symptoms, injuries, illnesses since your last visit?").

Death is an outcome of an SAE and usually not itself an SAE, unless it is death with no identifiable cause or event. In all other cases, record the cause of death as the SAE. Investigators will assess

the status of previously reported, and occurrence of new AEs and SAEs at all subject evaluation time points during the study.

10.2.1 Severity

Use the definitions found in the Common Toxicity Criteria for Adverse Events (CTCAE) v4.03 for grading the severity (intensity) of AEs. The CTCAE v4.03 displays Grades 1 through 5 with unique clinical descriptions of severity for each referenced AE and provides guidance not listed. Should a subject experience any AE not listed in the CTCAE v4.03, use the following grading system to assess severity:

- Grade 1 Mild; asymptomatic or mild symptoms; clinical or diagnostic observations only; intervention not indicated.
- Grade 2 Moderate; minimal, local or noninvasive intervention indicated; limiting ageappropriate instrumental activities of daily living (ADL), such as preparing meals, shopping for groceries or clothes, using the telephone, managing money, etc.
- Grade 3 Severe or medically significant but not immediately life-threatening; hospitalization
 or prolongation of hospitalization indicated; disabling; limiting self-care ADL, such as bathing,
 dressing and undressing, feeding self, using the toilet, taking medications, and not bedridden.
- Grade 4 Life-threatening consequences; urgent intervention indicated.
- Grade 5 Death related to AE.

10.2.2 Relationship to Study Treatment (Suspected Adverse Reactions)

Assess all AEs/SAEs for relationship to study treatment or if applicable, to study procedure.

To ensure consistency of AE and SAE causality assessments, investigators should apply the general guideline shown below. Multi-drug regimens should have a causality assessment of each component to aid in analysis.

Related (Suspected Adverse Reaction) A suspected adverse reaction means any AE for which there is a reasonable possibility that the drug caused the AE. Reasonable possibility means there is evidence to suggest a causal relationship between the drug and the AE such as a plausible temporal relationship between the onset of the AE and administration of the drug; and/or the AE follows a known pattern of response to the drug; and/or the AE abates or resolves upon discontinuation of the drug or dose reduction and, if applicable, reappears upon rechallenge. Further examples of type of evidence that would suggest a causal relationship between the drug and the AE:

- A single occurrence of an event that is uncommon and known to be strongly associated with drug exposure (eg, angioedema, hepatic injury, Stevens-Johnson Syndrome),
- One or more occurrences of an event that is not commonly associated with drug exposure, but is otherwise uncommon in the population exposed to the drug (eg, acute myocardial infarction in a young woman),
- An aggregate analysis of specific events observed in a clinical study (such as known consequences of the underlying disease or condition under investigation or other events that commonly occur in the study population independent of drug therapy) that indicates those events occur more frequently in the drug treatment group that in a concurrent or historical control group.

Not Related (Not Suspected) Adverse events that do not meet the definition above.

10.2.3 Pregnancy and Abortion

Report any pregnancy that occurs in a subject or male subject's female partner during the time between the first dose of study treatment and 60 days after the last dose of study treatment. Record any occurrence of pregnancy on the Pregnancy Exposure Report Form Part I and fax to Astex Pharmaceuticals Drug Safety within 24 hours of learning of the event. After the birth of the baby, collect additional information on the baby until the baby is 1 year old by completing the Pregnancy Exposure Report Form Part II.

A subject must immediately inform the investigator if the subject or subject's partner becomes pregnant during the time between the first dose of study treatment and 60 days after the last dose of study treatment. Any female subjects receiving study treatment who become pregnant must immediately discontinue study treatment. The investigator should counsel the subject, discussing any risks of continuing the pregnancy and any possible effects on the fetus.

Report any abortion and the reason for it, whether therapeutic, elective, or spontaneous, to Astex Pharmaceuticals Drug Safety within 24 hours, through the SAE reporting process (Section 10.3).

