- Subject is able to understand and comply with the study procedures, understand the risks involved in the study, and provide written informed consent before any study-specific procedure.
- 4. Women of childbearing potential (according to recommendations of the Clinical Trial Facilitation Group [CTFG]; see protocol Section 5.2 for details) must not be pregnant or breastfeeding and must have a negative pregnancy test at screening. Women of childbearing potential and men with female partners of childbearing potential must agree to practice 2 highly effective contraceptive measures of birth control (as described in Section 5.2) and must agree not to become pregnant or father a child while receiving guadecitabine and for at least 3 months after completing guadecitabine treatment.

Exclusion Criteria

Subjects meeting any of the following exclusion criteria will be excluded from the study:

 Any subject who, in the opinion of the investigator, may have other conditions, organ dysfunction, or have safety data from their prior study participation that suggest that the risks of continuing treatment with guadecitabine may outweigh the benefits.

Study Treatment:

Subjects will receive guadecitabine treatment at the same dose that they were receiving in the last cycle of their prior study or at a different dose as guided by the dose adjustment guidelines in the prior study protocol. Subsequent treatment delays and/or dose reduction are at the discretion of the investigator as guided by the dose adjustment guidelines of the prior study protocol. Treatment may continue as long as the subject continues to benefit based on investigator judgment.

There is no restriction on the use of best supportive care or hydroxyurea. Subjects who need to receive other anticancer therapies or other investigational treatments will be withdrawn from this study.

Study Endpoints:

Primary Endpoint

Safety as measured by adverse events.

Secondary Endpoint

Survival status.

Study Assessments and Procedures:

Informed consent and eligibility assessment (physical examination and hematology/laboratory assessments to judge continued favorable benefit/risk assessment) will be performed at screening.

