5.2 Inclusion Criteria

To be eligible for the study, subjects must fulfill all of the following inclusion criteria:

- Previous participation in an Astex-sponsored guadecitabine clinical trial (including but not limited to SGI-110-01, SGI-110-04, SGI-110-05, SGI-110-06, and SGI-110-07), in which the subject was treated with guadecitabine and was still on active treatment with guadecitabine at the time of database close for the prior study.
- Subject is considered to be benefitting from guadecitabine treatment in the opinion of the treating investigator.
- Able to understand and comply with the study procedures, understand the risks involved in the study, and provide written informed consent before any study-specific procedure.
- 4. Women of child-bearing potential (according to recommendations of the Clinical Trial Facilitation Group [CTFG]; see below* for details) must not be pregnant or breastfeeding and must have a negative pregnancy test at screening. Women of child-bearing potential and men with female partners of child-bearing potential must agree to practice 2 highly effective contraceptive measures while receiving treatment with guadecitabine and for at least 3 months after completing treatment and must agree not to become pregnant or father a child while receiving study treatment and for at least 3 months after completing guadecitabine treatment. Contraceptive measures which may be considered highly effective comprise combined hormonal contraception (oral, vaginal, or transdermal) or progestogen-only hormonal contraception (oral, injectable, implantable) associated with inhibition of ovulation, intrauterine device, intrauterine hormone-releasing system, bilateral tubal occlusion, sexual abstinence, and surgically successful vasectomy. Abstinence is acceptable only if it is consistent with the preferred and usual lifestyle of the subject. Periodic abstinence (eg, calendar, ovulation, symptothermal, or postovulation methods) and withdrawal are not acceptable methods of birth control.

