8.3 Fertility

Decitabine, the active metabolite of guadecitabine, alters fertility and is mutagenic. Because of the possibility of infertility, men should have sought advice on cryopreservation of sperm, and women of childbearing potential should have sought consultation regarding oocyte cryopreservation before study treatment was started in the prior study. Women of child-bearing potential must not be pregnant or breastfeeding and must have a negative pregnancy test at screening. Women of child-bearing potential and men with female partners of child-bearing potential must agree to practice 2 highly effective contraceptive measures of birth control and must agree not to become pregnant or father a child while receiving treatment with guadecitabine and for at least 3 months after completing treatment.

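### Pregnancy reporting stops 60 days after the last dose, about a month before the 3-month pregnancy-avoidance period ends (low priority)

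*Protocol*

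**What the plan says.** Protocol Section 10.2.3 uses the same window twice, for the investigator's report to the sponsor and for the subject's duty to tell the investigator. Both apply to a pregnancy in a subject or a male subject's partner "during the time between the first dose of study treatment and 60 days after the last dose of study treatment". On the subject's side: "A subject must immediately inform the investigator if the subject or subject's partner becomes pregnant" within that window. A reported pregnancy leads to infant follow-up, in which the site is to "collect additional information on the baby until the baby is 1 year old".

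The avoidance period is longer. In the synopsis, women of childbearing potential and men with partners of childbearing potential "must agree not to become pregnant or father a child while receiving guadecitabine and for at least 3 months after completing guadecitabine treatment". Section 5.2 repeats this: they "must agree not to become pregnant or father a child while receiving study treatment and for at least 3 months after completing guadecitabine treatment". Section 8.3 sets the same 3-month minimum and says that decitabine, the active metabolite, "alters fertility and is mutagenic".

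Two other routes can bring a late case to the sponsor:

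- **Abortions.** Section 10.2.3 says "Report any abortion and the reason for it, whether therapeutic, elective, or spontaneous", through the SAE process and with no stated end date.
- **Related SAEs.** Section 10.3 keeps these reportable after day 30 with no end date, and Section 10.1.2 lists "A congenital anomaly or birth defect" among the serious outcomes.

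**The concern.** The sponsor treats at least the first 3 months after the last dose as a period in which conception should be avoided, yet stops asking to hear about conceptions after day 60. No section explains the shorter window.

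After day 60 there is little else to bring a pregnancy to light. The last scheduled contact is the safety visit, 30 ± 7 days after the last dose or earlier if alternative therapy starts, and the subject then leaves the study (Section 4.1). Table 1 schedules no later visit or pregnancy test, and partners of male subjects are not tested at all. A later pregnancy is therefore learned of mainly because Section 10.2.3 obliges someone to report it.

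At stake are the completeness of exposure and infant follow-up data for a drug with a mutagenic metabolite, and the investigator's chance to counsel the subject, which Section 10.2.3 asks for but which depends on being told. Nothing in the statistical analysis is at stake.

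**Working it through.** The plan gives no figure to reproduce. The check compares two time windows.

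**Inputs.** Reporting limit: 60 days after the last dose (Section 10.2.3). Avoidance limit: at least 3 months (synopsis, Sections 5.2 and 8.3). Three calendar months are 89 to 92 days. The SAP's month of 30.4375 days (Section 5.1) gives 3 × 30.4375 = 91.3 days.

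**Gap.** Avoidance minus reporting:
- 89 − 60 = 29 days and 92 − 60 = 32 days; with the SAP month, 91.3 − 60 = 31.3 days.
- Share of the minimum post-treatment period: 29/89 = 32.6% to 32/92 = 34.8%.

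Because the period is stated as a minimum, this is the smallest gap. A pregnancy that begins by day 60 and is recognised later is still covered.

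**Share of the whole avoidance period, treatment included.** Treatment lasting 1 to 3 years is an assumption:
- 1 year: 32/(365.25 + 92) = 7.0%.
- 3 years: 29/(1095.75 + 89) = 2.4%.

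These are not bounds. Shorter treatment raises the share, towards 33–35% for a subject who stops almost at once.

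**Expected pregnancies in the gap.** Subjects × fraction of reproductive potential × annual pregnancy rate × gap in years. The 250 subjects are the protocol's planning figure. The 5–20% of reproductive potential and 1–5% pregnancies per year are assumptions, not in the documents:
- Low: 250 × 0.05 × 0.01 × 29/365.25 = 0.01.
- High: 250 × 0.20 × 0.05 × 32/365.25 = 0.22.

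This probably overstates the count, since it lets all 250 subjects live through the gap, while Section 2.1 says death is the most common outcome.

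**What the other routes leave out.** An abortion, or a birth defect judged related, would be reportable. An ongoing pregnancy, an uncomplicated birth, or an outcome judged unrelated would not.

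**Time without scheduled contact.** From a safety visit on day 23–37 to the end of the reporting duty is 60 − 37 = 23 to 60 − 23 = 37 days now. It would be 89 − 37 = 52 to 92 − 23 = 69 days under a 3-month limit, and longer if alternative therapy brings the visit forward.

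**Separate editorial note on the same follow-up period.** The synopsis, Sections 4.1 and 5.4.1 and Table 1 allow the safety visit at 30 ± 7 days, while Section 9.3.4 asks for follow-up of at least 30 (+7) days. A day-23 visit leaves 30 − 23 = 7 days (7/30 = 23%) without scheduled contact; a visit on day 30 or later leaves none. The duties to record AEs and report SAEs to day 30 (Sections 10.2 and 10.3) hold either way.

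**The case against.** The two windows do different jobs. The avoidance period is a precaution stated as a minimum; Section 10.2.3 is a reporting duty. Nothing in the protocol says they must be equal, a site can comply with both, and Section 10.2.3 does not bar a later report. This is right, and it is why the point is a design choice and not an error.

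The gravest outcomes also have a route already. Under Section 10.2.2 a plausible temporal relationship can be enough to call an event related, so a birth defect after conception within 3 months of dosing could well qualify as a reportable SAE. That narrows the gap but does not close it: it depends on the site learning of the birth, and it does not capture pregnancies as exposures or start infant follow-up.

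The expected yield is close to zero and the count rests on assumed inputs. This stands and keeps the priority low.

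Timing is the strongest practical objection. The SAP of 3 November 2021 is still based on the January 2018 protocol, describes enrollment in the past tense and plans its analyses for the end of the study. The documents do not say whether dosing had ended, and they foresee no further amendment. If no subject is within 3 months of the last dose, amending this protocol would achieve nothing. The extra month would in any case be passive reporting by people who have left the study.

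The visit-window note concerns AE contact, not pregnancy, and identifies no lost duty. It is kept only as an editorial remark.

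**Conclusion.** The mismatch is real in the current protocol text. The reporting and notification duties end 29 to 32 days before the minimum avoidance period does, which leaves its last third uncovered except for abortions and related SAEs. That result rests only on the two stated limits and the length of three calendar months. The pregnancy count (0.01 to 0.22) and the 2–7% share of the whole period are illustrations on assumed inputs. The consent form is not in the reviewed text, so subjects may be told something different there. No endpoint, analysis set or analysis changes. This is an optional, low-priority safety improvement.

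**What to change.** Change both 60-day limits in Section 10.2.3 to at least 3 months after the last dose, to match the synopsis, Section 5.2 and Section 8.3, and update the consent form if it carries the shorter limit. Under Section 14.4 this is a protocol amendment with IRB/IEC submission, planned for about 150 centers in about 20 countries, so it is better combined with another amendment, if there is one, than issued alone. The running cost is about one more month of passive reporting after subjects have left, with no new visits, tests or analyses. If follow-up is already complete, carry the wording into later guadecitabine protocols instead.

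Separately, as an editorial matter, use 30 (+7) days in the synopsis, Sections 4.1 and 5.4.1 and Table 1, except where alternative therapy starts earlier, or add a telephone AE contact on or after day 30 when the visit was earlier. An Administrative Letter may be enough, since Section 14.4 lets these correct inconsistencies. The cost is slightly later visits or an occasional call.
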